9.2 The WOMAC (Western Ontario and McMaster Universities) Index of

Osteoarthritis

Overview:

The WOMAC (Westren Ontario and McMaster Universities) index is used to assess patients with

osteoarthritis of the hip or knee using 24 parameters. It can be used to monitor the course of the disease or to determine the effectiveness of anti-rheumatic medications.

Pain:

- (1) walking
- (2) stair climbing
- (3) nocturnal
- (4) rest
- (5) weight bearing

Stiffness:

- (1) morning stiffness
 - (2) stiffness occurring later in the day
- Physical function:

- (1) descending stairs
- (2) ascending stairs
- (3) rising from sitting
- (4) standing
- (5) bending to floor
- (6) walking on flat
- (7) getting in or out of car
- (8) going shopping
- (9) putting on socks
- (10) rising from bed

- (11) taking off socks
- (12) lying in bed
- (13) sitting
- (14) sitting
- (15) getting on or off toilet
- (16) heavy domestic duties
- (17) light domestic duties

While the index was being developed performance of social functions and the status of emotional function were also included. These were not included in the final instrument.

Social function:

- (1) leisure activities
- (2) community events
- (3) church attendance
- (4) with spouse
- (5) with family
- (6) with friends
- (7) with others

Emotional function:

- (1) anxiety
- (2) irritability
- (3) frustration
- (4) depression
- (5) relaxation
- (6) insomnia
- (7) boredom
- (8) loneliness
- (9) stress
- (10) well-being

Scoring and Interpretation

Response	Points
none	0
slight	1
moderate	2
severe	3
extreme	4

Alternatively a visual analogue scale (VAS) may be used ranging from 0 to 10. score

=

= SUM(points for relevant items) average score =

= (total score) / (number of items) Interpretation:

- minimum total score: 0
- maximum total score: 96
- minimum pain subscore: 0
- maximum pain subscore: 20
- minimum stiffness subscore: 0
- maximum stiffness subscore: 8
- minimum physical function subscore: 0
- maximum physical function subscore: 68

9.3 Modified Score for the Assessment and Quantification of Chronic Rheumatoid Affections of the Hands (M-SACRAH)

PART 1: DIFFICULTIES PERFORMING DAILY ACTIVITIES

Think about the **difficulties** you have had in the past 48 hours doing the following physical daily activities **because of your finger joint problems**. This means your ability to **move easily and do things yourself**. (Please mark each answer with an “X” on the line.)

QUESTION: How difficult was it for you...

1. To unlock the front door with a key?

No difficulty _____ Impossible

2. To button or unbutton buttons?

No difficulty _____ Impossible

3. To turn on the faucet?

No difficulty _____ Impossible

4. To zip or unzip a zipper?

No difficulty _____ Impossible

5. To tie shoelaces?

No difficulty _____ Impossible

6. To unscrew and screw on the toothpaste cap?

No difficulty _____ Impossible

7. To turn the pages of the newspaper?

No difficulty _____ Impossible

8. To write by hand?

No difficulty _____ Impossible

PART 2: STIFFNESS

Think about the **stiffness** (not pain) you have had in the past 48 hours because of your **finger joint problems**. Joint

stiffness is normally experienced as a **limitation or reduction in the mobility of your joints**.

(Please mark each answer with an “X” on the line.)

QUESTION:

9. How **severe** was your joint stiffness **after you first woke up** in the morning?

No stiffness _____ Unbearable stiffness

10. How **severe** was your joint stiffness later in the day after your hands had been at rest for a while?

No stiffness _____ Unbearable stiffness

PART 3: PAIN

Think about the pain you have had in the past 48 hours because of your finger joint problems.

(Please mark each answer with an “X” on the line.)

QUESTION: How severe was your pain...

11. During your work activities or difficult house chores?

No pain _____ Unbearable pain

12. When your hands were at rest in the evening?

No pain _____ Unbearable pain

9.5 Questionnaire on Nurses' Knowledge, Beliefs, and Practices Regarding the Management of Musculoskeletal Symptoms in Breast Cancer Patients

Undergoing Endocrine Therapy in a Multicultural Context

We are conducting a study on the differences in nurses' knowledge, attitudes, and practices regarding the management of musculoskeletal symptoms in breast cancer patients undergoing endocrine therapy in a multicultural context. We sincerely invite you to participate in this research. If you agree to take part, you will be asked to complete a four-part questionnaire, which is expected to take approximately 15-20 minutes. Your participation will greatly contribute to our understanding and improvement of the quality of care for breast cancer patients.

There are no known risks associated with this study. All data collected will be anonymized and kept strictly confidential. You are free to withdraw from the study at any time without providing any reason. We greatly appreciate your support and participation.

Part I: Basic Information

1. Name of your workplace: _____

2. Your gender [Single choice question]

A. Male

B. Female

3. Your age: _____

4. Years of nursing experience: _____ years

5. Your current professional title [Single choice question]

- A. Nurse
- B. Registered Nurse
- C. Charge Nurse
- D. Deputy Head Nurse
- E. Head Nurse
- F. Other: _____

6. Your highest academic degree [Single choice question]

- A. Junior college and below
- B. Bachelor's degree
- C. Master's degree or Postgraduate diploma
- D. Doctoral degree and above

7. The number of beds in your department is: _____

8. Your working city [Single choice question]

- A. Shanghai
- B. Dali
- C. Indonesia
- D. Other: _____

9. Are you familiar with the clinical guidelines for the management of musculoskeletal symptoms among breast cancer patients with endocrine therapy?

[Single choice question]

- A. Yes
- B. No

10. Does your institution have an internal implementation plan or process for the management of musculoskeletal symptoms among breast cancer patients with endocrine therapy? [Single choice question]

- A. Yes
- B. No

11. Have you participated in training related to the management of musculoskeletal symptoms among breast cancer patients with endocrine therapy? [Single choice question]

- A. Yes
- B. No

12. If you have **not** received the relevant training, what are the reasons? [Multiple choice question]

- A. Heavy workload in the department, no time or energy
- B. Lack of interest, training is not a concern
- C. Unaware of such training notifications and information
- D. Low seniority, no opportunity or quota to participate in training

13. If you have received the relevant training, what type of training have you received? [Multiple choice question]

- A. Training organized by the department
- B. Training organized by the hospital
- C. Training organized by external organizations
- D. Other: _____

14. What are your main sources for acquiring knowledge about endocrine therapy for breast cancer patients? [Multiple choice question]

- A. Institutional education
- B. Relevant books and literature
- C. Academic conferences or lectures
- D. Departmental business learning
- E. Self-study due to personal interest or work requirements
- F. Training courses
- G. Have not yet paid attention to this knowledge area

15. Do you think it is necessary to learn and master more knowledge about the management of musculoskeletal symptoms among breast cancer patients with endocrine therapy? [Single choice question]

A. Yes

B. No

Part II: Knowledge (K)

1. Which of the following adverse reactions are most common in endocrine therapy for breast cancer patients? [Multiple choice question]

A. Hot flashes and sweating

B. Musculoskeletal pain

C. Decreased bone density, increasing the risk of fractures

D. Vaginal dryness and decreased libido

E. Endometrial thickening, potentially increasing the risk of endometrial cancer

F. Liver function abnormalities, such as elevated transaminases

G. Cardiovascular events, such as thrombosis

2. Which factors may exacerbate musculoskeletal symptoms during endocrine therapy for breast cancer patients? [Multiple choice question]

A. Weight gain

B. Prolonged sedentary behavior

C. Insufficient intake of calcium and vitamin D

D. Lack of regular exercise

3. What is the recommended daily calcium intake during endocrine therapy for breast cancer patients? [Single choice question]

A.1000mg

B.1200mg

C.1500mg

D.2000mg

4. What is the recommended daily vitamin D intake during endocrine therapy for breast cancer patients? [Single choice question]

A.400IU

B.800IU

C.1000IU

D.2000IU

5. Vitamin D is crucial for the skeletal health of breast cancer patients with endocrine therapy. Which of the following is the primary function of vitamin D? [Single choice question]

- A. Promotes calcium absorption and maintains bone health
- B. Enhances muscle function
- C. Regulates the immune system
- D. Improves cardiovascular health

6. Which of the following foods helps prevent osteoporosis? [Single choice question]

- A. Milk and dairy products
- B. Green leafy vegetables
- C. Nuts and seeds
- D. Fish (such as salmon)

7. Which mineral helps maintain bone health? [Single choice question]

- A. Magnesium
- B. Iron
- C. Zinc
- D. Calcium

8. Which of the following behaviors is most beneficial to bone health? [Single choice question]

- A. Vitamin D and calcium supplementation
- B. Prolonged bed rest
- C. Restricting fat intake
- D. High-fiber diet

9. What is the recommended frequency for bone density tests in breast cancer patients with endocrine therapy? [Single choice question]

- A. Every 6 months
- B. Annually
- C. Every 2 years

D. Every 5 years

10. What is the purpose of regular bone density testing during endocrine therapy for breast cancer patients? [Single choice question]

- A. Monitoring blood sugar levels
- B. Assessing bone health status
- C. Measuring blood pressure
- D. Checking vision

11. Which medication is commonly used to alleviate joint pain caused by endocrine therapy for breast cancer? [Single choice question]

- A. Nonsteroidal anti-inflammatory drugs (NSAIDs)
- B. Calcium and vitamin D supplements
- C. Bisphosphonates
- D. Opioids

12. Which type of physical therapy can help breast cancer patients with endocrine therapy to alleviate musculoskeletal symptoms? [Single choice question]

- A. Yoga
- B. Swimming
- C. Specific exercises under the guidance of physical therapy
- D. Heat therapy

13. How many minutes of moderate-intensity aerobic exercise should adults engage in per week during endocrine therapy for breast cancer? [Single choice question]

- A. 75 minutes
- B. 150 minutes
- C. 225 minutes
- D. 300 minutes

14. Which of the following behaviors helps maintain bone health during endocrine therapy for breast cancer? [Single choice question]

- A. Engaging in regular moderate-intensity exercise
- B. High-sugar diet

- C. Prolonged bed rest
 - D. Restricting calcium intake
-

-----**Part III: Attitude (A)**

1. Do you think managing the musculoskeletal symptoms of breast cancer patients is important? [Single choice question]

- A. Extremely important
- B. Important
- C. Moderately important
- D. Unimportant
- E. Extremely unimportant

2. Do you think nurses play a crucial role in managing the musculoskeletal symptoms of breast cancer patients? [Single choice question]

- A. Strongly agree
- B. Agree
- C. Uncertain
- D. Disagree
- E. Strongly disagree

3. What kind of knowledge do you think nurses need to have to manage musculoskeletal symptoms caused by endocrine therapy for breast cancer? [Multiple choice question]

- A. Symptom recognition
- B. Medication management
- C. Physical therapy
- D. Nutritional guidance
- E. Exercise advice
- F. Other: _____

4. Are you willing to receive training on the management of musculoskeletal symptoms related to endocrine therapy for breast cancer? [Single choice question]

- A. Very willing
- B. Willing

- C. Uncertain
- D. Unwilling
- E. Very unwilling

5. Do you think the current training is sufficient to meet the needs of patients with endocrine therapy for breast cancer? [Single choice question]

- A. Strongly agree
- B. Agree
- C. Uncertain
- D. Disagree
- E. Strongly disagree

6. What do you think are the main challenges in managing musculoskeletal symptoms in actual work? [Multiple choice question]

- A. Low patient compliance
- B. Lack of professional knowledge
- C. Lack of practical experience
- D. Insufficient hospital support
- E. Other: _____

7. Do you think it is necessary to establish a specialized management plan for musculoskeletal symptoms? [Single choice question]

- A. Strongly agree
- B. Agree
- C. Uncertain
- D. Disagree
- E. Strongly disagree

8. How much do you think musculoskeletal symptoms affect the quality of life of breast cancer patients? [Single choice question]

- A. Very significant
- B. Significant
- C. Moderate
- D. Slight

E. Very slight

9. What do you think are the main responsibilities of nurses in managing musculoskeletal symptoms? [Multiple choice question]

A. Assessing and monitoring symptoms

B. Providing education and guidance

C. Developing and implementing management plans

D. Collaborating with physicians and other healthcare team members

E. Other: _____

10. Do you believe that health education can effectively improve patient compliance with musculoskeletal symptom management? [Single choice question]

A. Strongly agree

B. Agree

C. Uncertain

D. Disagree

E. Strongly disagree

-----**Part IV: Practice (P)**

1. Do you actively assess the musculoskeletal symptoms of breast cancer patients in your daily nursing practice? [Single choice question]

A. Never

B. Occasionally

C. Sometimes

D. Often

E. Always

2. Do you provide health education on musculoskeletal symptom management to breast cancer patients and their families? [Single choice question]

A. Never

B. Occasionally

C. Sometimes

D. Often

E. Always

3. Do you tailor musculoskeletal symptom management plans to the individual patient's situation in your actual work? [Single choice question]

- A. Never
- B. Occasionally
- C. Sometimes
- D. Often
- E. Always

4. Do you regularly review and adjust the musculoskeletal symptom management plans for patients? [Single choice question]

- A. Never
- B. Occasionally
- C. Sometimes
- D. Often
- E. Always

5. Do you collaborate with other healthcare team members to jointly manage the musculoskeletal symptoms of breast cancer patients? [Single choice question]

- A. Never
- B. Occasionally
- C. Sometimes
- D. Often
- E. Always

6. Do you regularly participate in relevant training or learning to improve your knowledge and skills in musculoskeletal symptom management? [Single choice question]

- A. Never
- B. Occasionally
- C. Sometimes
- D. Often
- E. Always

7. Do you proactively learn and apply new technologies and methods in musculoskeletal symptom management in your work? [Single choice question]
- A. Never
 - B. Occasionally
 - C. Sometimes
 - D. Often
 - E. Always
8. Do you record the patient's compliance in managing musculoskeletal symptoms? [Single choice question]
- A. Never
 - B. Occasionally
 - C. Sometimes
 - D. Often
 - E. Always
9. Do you participate in the establishment and (or) strict implementation of the unit's processes and standards for managing musculoskeletal symptoms in breast cancer patients? [Single choice question]
- A. Never
 - B. Occasionally
 - C. Sometimes
 - D. Often
 - E. Always
10. Do you regularly assess and improve your nursing practice to enhance the quality of care for breast cancer patients? [Single choice question]
- A. Never
 - B. Occasionally
 - C. Sometimes
 - D. Often
 - E. Always

11. Do you share your experience and skills in managing musculoskeletal symptoms with new nurses or interns? [Single choice question]

- A. Never
- B. Occasionally
- C. Sometimes
- D. Often
- E. Always

-----Thank you very much for your participation! Your answers will provide valuable insights for our study!

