4.1.2 Practitioner Outcomes

- **Target Population:** Nurses and clinical practitioners involved in managing musculoskeletal symptoms in breast cancer patients.
- **Assessment Tool:** The “Survey on Nurses' Knowledge, Attitude, and Practice (KAP) Regarding Musculoskeletal Symptom Management in Breast Cancer Patients Undergoing Endocrine Therapy in a Multicultural Context.” Pre- and post-intervention comparisons will be conducted to assess knowledge, attitudes, and practice skills.

- **Expected Outcomes:** Nursing staff will demonstrate significant improvements in knowledge, beliefs, and practical skills in managing musculoskeletal symptoms, promoting evidence-based nursing practices.

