9.1 Baseline Survey Form - Musculoskeletal Symptom Form

Dear Patients,

In order to better understand your condition during endocrine therapy and to help us provide you with appropriate treatment and care, we have designed the following questionnaire to assess your physical and psychological status. The information you provide will serve as a valuable reference for clinical medical and nursing work. We kindly ask that you fill out the questionnaire thoroughly, reflecting your true situation. Some questions may be completed by medical personnel on your behalf.

We sincerely thank you for your participation, support, and cooperation!

- *There are no right or wrong answers. Please respond based on how you usually feel and act.*
- *Please fill out the form based on your actual situation.*
- *For items with a ☐, please place a "✓" in the appropriate box.*

☐ **Outpatient** ☐ **Inpatient**

Outpatient/Inpatient Number: _____

Enrollment/Follow-up Date: _____

Investigator's Signature: _____

I. General Information

1. Gender:

☐ Male ☐ Female

2. Age: _____ years

3. Height: _____ cm Weight: _____ kg

4. Religious Belief:

☐ None ☐ Buddhism ☐ Christianity ☐ Islam ☐ Other

5. Do you regularly participate in religious activities or prayer?

☐ Never ☐ Occasionally ☐ Sometimes ☐ Frequently

6. How much does your religious belief influence your lifestyle?

☐ No influence ☐ Slight influence ☐ Some influence ☐ Significant influence

7. Educational Level:

☐ Primary school or below
☐ Middle school
☐ Technical school/High school
☐ College/University
☐ Graduate degree or higher

8. Employment Status:

☐ Unemployed ☐ Part-time job ☐ Full-time job ☐ Retired ☐ Homemaker

9. Marital Status:

☐ Single ☐ Married ☐ Divorced ☐ Widowed

10. Living Situation:

☐ Stable ☐ Unstable ☐ Homeless

11. Medical Expenses:

☐ Fully self-paid
☐ Mostly self-paid
☐ Partially self-paid
☐ No self-payment

12. Economic Pressure:

☐ None ☐ Slight ☐ Some ☐ Significant

13. Understanding of your disease:

☐ Not at all ☐ Slightly ☐ Somewhat ☐ Very well

II. Medical History

1. Diagnosis Date: _____ Year _____ Month

2. Surgical Approach: _____

3. Pathological Type: _____ (e.g., ductal carcinoma, lobular carcinoma, ductal carcinoma in situ, lobular carcinoma in situ, inflammatory breast cancer, mucinous carcinoma, medullary carcinoma) (may consult healthcare professionals for completion)

4. Comprehensive Treatment Plan:

☐ Chemotherapy: _____ ☐ Radiotherapy: _____

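### Nurse KAP is to be compared before and after the intervention, but the printed form makes no provision for linking a nurse's two responses

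*Protocol*

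**What the plan says.** Section 4.1.2 makes practitioner KAP one of three outcome levels. It states that "Pre- and post-intervention comparisons will be conducted to assess knowledge, attitudes, and practice skills" and gives the expected result: "Nursing staff will demonstrate significant improvements in knowledge, beliefs, and practical skills in managing musculoskeletal symptoms". It does not say whether the comparison is paired, and the protocol gives no number of nurses, standard deviation or target change for KAP.

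The questionnaire is printed in full in section 9.5. Its introduction tells nurses that "you will be asked to complete a four-part questionnaire, which is expected to take approximately 15-20 minutes", that "All data collected will be anonymized and kept strictly confidential", and that "You are free to withdraw from the study at any time without providing any reason". It mentions neither a second completion nor any linkage of answers.

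Part I asks for "Name of your workplace", gender, age, "Years of nursing experience", professional title, highest degree, number of beds and city. There is no field for a name, staff number, study number or code. The patient baseline form in section 9.1, by contrast, has a field for "Outpatient/Inpatient Number".

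**The concern.** A before-and-after comparison in the same people draws its precision from each person serving as their own control, and that needs something on the form to join the two records. The analysis plan can choose between a paired and an unpaired method, but it cannot recover a link that the instrument did not collect.

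Two things are at stake. The first is precision: unlinked waves can only be given the standard error of two independent samples. The second is interpretation. Section 4.1.2 attributes the expected improvement to the nursing staff. If some nurses answer only once, the difference between waves mixes learning with a change in who answered, and without a link nobody can see how much of each there is.

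**Working it through.** The protocol states no KAP figure, so there is nothing to reproduce. The correlation ρ, the number of nurses n and the size of change used below are all assumptions for illustration. σ is the SD of the KAP score, taken as equal at both waves.

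**Precision, same n nurses at both waves**

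The estimated mean change is the same with or without a link. What differs is the variance that can be attached to it:

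- Treated as independent: 2σ²/n
- Paired: 2σ²(1−ρ)/n
- Ratio of variances: 1/(1−ρ); ratio of standard errors: 1/√(1−ρ)

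| Assumed ρ | Variance ratio | SE ratio |
|---|---|---|
| 0 | 1.00 | 1.00 |
| 0.3 | 1/0.7 = 1.43 | 1.20 |
| 0.5 | 1/0.5 = 2.00 | 1.41 |
| 0.7 | 1/0.3 = 3.33 | 1.83 |

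**Direction of the error**

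A nominal two-sided 5% test that ignores the pairing has true type I error 2[1−Φ(1.96/√(1−ρ))]. This is about 1.9%, 0.6% and 0.03% at ρ = 0.3, 0.5 and 0.7. The test is conservative.

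**Power, illustration with n = 30 and a true change of 0.5 SD**

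- Unlinked SE: √(2/30) = 0.258 SD. The test rejects when the mean change exceeds 1.96 × 0.258 = 0.506 SD, just above the true change of 0.5, so power is about 49%.
- Paired SE: √(2(1−ρ)/30) = 0.216, 0.183 and 0.141 SD at ρ = 0.3, 0.5 and 0.7. Power is Φ(0.5/SE − 1.96) = 64%, 78% and 94%.

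**Partial overlap**

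If each wave has n responders and only a share q of them answers both times, the variance of the difference in means is 2σ²(1−qρ)/n. At q = 1 this is the paired variance; at q = 0 the waves are independent and treating them so loses nothing. Without a code q is unknown, so the right standard error is unknown too. For positive ρ it lies between the two cases above.

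**Who responds**

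Suppose the true change is Δ, and the second-wave responders had a baseline mean that differed by δ from that of all first-wave responders. The unlinked difference then estimates Δ + δ. With a code, δ can be examined by comparing the baseline scores of nurses who answered twice with those of nurses who answered once. Without one, Δ and δ cannot be separated. This does not depend on ρ.

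**The case against.** The strongest reply is that the protocol nowhere rules linkage out.

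- **Anonymised may mean coded.** The promise may describe handling after collection, with a key kept elsewhere. Consent pages are not in the text under review, so a separate nurse information sheet or coding instruction is possible. This stands, and it is why a reader who infers that pairing is impossible goes too far. It remains true that the protocol describes no key and the printed form has no place for a code.
- **The demographic items could serve as a match.** Workplace, age, experience, title and degree would probably match some nurses, more easily where few respond. That stands in part. Age, experience and title can all change between waves, so matching would be error-prone. Where it succeeded, it would show that the answers are re-identifiable, which weakens the anonymity promise.
- **The same nurses may not answer twice.** Section 4.1.2 does not state a fixed cohort, and the questionnaire's introduction would also suit the cross-sectional survey in objective 2.1. If the waves are separate samples, an unpaired analysis is correct and the precision argument falls away. This stands; the precision argument is conditional on repeat responders.
- **The choice of test belongs in the analysis plan.** Agreed, but the form and its wording to participants are fixed in this protocol.

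A reader might also infer that the error bars would produce a spurious improvement, or that the nurse sample is small. The documents support neither. Ignoring a positive correlation makes the test conservative, and no nurse number is given.

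**Conclusion.** The point holds as a minor one. The protocol commits to a before-and-after KAP comparison and prints a form with no linking code, an anonymity promise and mention of one completion only, so no provision is made for pairing.

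If the same nurses answer twice, the correlation is positive and the forms are not reliably linked, the variance attached to the mean change is 1.4 to 3.3 times the paired variance for assumed ρ from 0.3 to 0.7. The actual loss cannot be derived from the protocol, because the number of nurses, the SD and the correlation are not stated. The consequence is lost power. The inability to separate learning from a change in respondents applies whatever the correlation.

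Only the practitioner outcome is touched. The patient sample size and the WOMAC comparison do not depend on it.

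**What to change.** Before the baseline wave:

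1. Add a self-generated code field to the section 9.5 questionnaire, to be completed in the same way at both waves.
2. Revise the introduction to tell nurses that they will be asked to complete the form a second time, and that answers are held under a code without names.
3. State in section 4.1.2 that within-nurse change will be analysed with site as a factor, and that the number of nurses answering both waves will be reported.

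The cost is one field and a short change to the participant wording. The downside is slightly weaker anonymity, although the present demographic items already limit it.

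If baseline forms have already been collected without a code, say so and report the comparison as unpaired. Note that its standard error is conservative for any nurses who answered twice, and that a change in respondents cannot be excluded.
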